3.2 Schedule of Visits and Procedures Study

All subjects who are randomized and take any SM will be followed according to the protocol regardless of the number of doses of SM taken, unless consent for follow-up is withdrawn. [Table 1](#) below presents the Schedule of Visits and Procedures for the study.

Table 1: Schedule of Visits and Procedure

Period	Screening	Treatment Phase			
		Titration		Maintenance	
		Baseline, Randomization			End of Study ⁱ
Visit Number	1	2	3, 4	5-9	10
Visit Day		1	7, 14	21, 28, 35, 42, 49	56
Visit Window (days)	≤28d before V2		±2	±2	±2
Informed Consent/Accent (if applicable) ^a	X				
Medical and Psychiatric History	X				
Mini-KID	X				
Demographics	X				
Urine Drug Screen	X				
Randomization		X			
Physical Exam ^b	X				X ^c
Inclusion/Exclusion Criteria	X	X			
ECG (12-lead)	X				X
Vital Signs ^d	X	X	X	X	X
Hematology	X				X
Serum Chemistry	X				X

Pharmacogenomic sample	X				
Urine Pregnancy test, FOCP only		X			X
CGI-S	X	X			
CGI-I			X	X	X
C-SSRS	X	X	X	X	X
ADHD-RS-5	X	X	X	X	X
WFIRS-P, PSI-4-SF		X			X
Conners 3 ^e – parent, self		X			X
Concomitant Medication	X	X	X	X	X
Adverse Events		X ^f	X	X	X ^f
Drug Dispensed		X ^g	X	X	
Drug Return, Compliance			X	X	X
Optional PK Blood Sampling ^h			X	X	X

a To be obtained prior to performing any study procedures.

b Includes height and weight, excludes genitourinary system

c Changes from Screening only

d Seated (5 min) heart rate and blood pressure, temperature, respiratory rate

e Self report = 8-11 year olds only

f At Baseline, AEs are recorded only after SM is administered. Subjects with serious adverse events at EOS will be followed until the event has resolved or considered stable.

g Titration will begin after first dose of SM is administered

- ^h An optional PK substudy will take place between Visits 3 and 10, inclusive. Samples will be taken pre-dose and post-dose at Hours 1, 2, 4, and 6.
- ⁱ EOS or last visit in the case of early discontinuation.

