3.3 Procedures for Discontinuing Treatment and Removal of Subjects from Study

Subjects will be considered to have completed the study if they complete all visits up to and including Week 8 (EOS).

All subjects who discontinue early will complete the procedures listed for Week 8 (EOS).

All reasons for screening failure will be recorded. If the subject passes screening but fails eligibility at Baseline, the reason(s) will also be recorded.

The Investigator(s) or subjects themselves may stop SM treatment at any time for safety or personal reasons. A subject is free to withdraw from the study at any time for any reason without prejudice to their future medical care by the physician or at the institution. The Sponsor may also withdraw the subject at any time in the interest of subject safety. The withdrawal of a subject from the study should be discussed where possible with the Medical Monitor and/or Clinical Research Associate (CRA) before the subject stops SM. Subjects removed from the study for any reason will not be replaced.

Reasons for subject discontinuation may include:

- Withdrawal of consent
- Noncompliance
- Occurrence of unmanageable AEs
- Lost to follow-up
- Other

The primary reason for subject discontinuation must be recorded in the subject's medical record and on the eCRF. If a subject is withdrawn for more than one reason, each reason should be documented in the source document and the most medically significant reason should be entered on the eCRF.

If a subject misses doses of SM during this study, the Investigator shall counsel the subject/caregiver on the importance of compliance. If the subject has consistently missed doses, he or she may be discontinued from the study at the discretion of the Investigator and in consultation with the Medical Monitor; all procedures for discontinuation will be followed.

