6.1 General Principles

All statistical analysis will be performed using SAS version 9.2 or higher by [REDACTED], which is the designated CRO. [REDACTED] will be responsible for creating TLF reports by SAS programming and delivering the reports as well as the programs to Supernus at the completion of the study.

All tabulations of analysis results will include summaries for the following three treatments: SPN-812 ER 400 mg, SPN-812 ER 200 mg, and placebo.

Where appropriate, variables will be summarized descriptively (frequency count and percent for categorical variables, and number of subjects (n), mean, standard deviation (SD), median, minimum, and maximum for continuous variables).

Means, least-squares (LS) means and medians will be presented to 1 more decimal place than the recorded data. Standard deviations and standard errors will be presented to two (2) more decimal places than the recorded data. Minimum and maximum values will be presented using the same number of decimal places as the recorded data. Confidence intervals will be presented using the same number of decimal places as the parameters (e.g., mean). Percentages will be presented to one (1) decimal place. P-values will use four decimal places.

Categorical variables will be analyzed using categorical response methods such as Pearson's Chi-square test. If expected frequencies are too small for asymptotic assumptions, exact testing techniques will be used.

The data summaries will be accompanied by individual subject data listings, as specified in Sections 16.2 and 16.4 of ICH Guidance E3, sorted by unique subject identifier. All data available from the electronic case report forms (eCRFs) will be listed. Unscheduled measurements will be excluded from the descriptive statistics and statistical analysis but will be included in listings. The

“EARLY_TERMINATION VISIT” for early discontinued subjects will be assumed to correspond to Visit 10 for statistical summaries but displayed as is in listings.

Derived analysis datasets will be produced from the SDTM data. Specifications for derived datasets will be developed. Analysis datasets to be created will include ADQS (Questionnaire analysis dataset), ADEFF1 and ADEFF2 (efficacy analysis dataset2), ADSL (subject-level analysis dataset), ADAE (Adverse event analysis dataset) and other as appropriate.

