The ADEFF1 analysis dataset will be used for programming the primary analysis table and will contain variables for Subject ID, BASE (Baseline (Visit 2)), AVAL (values at Visit 3 –Visit 10), CHG (for CFB), ITT Flag variable, Treatment, and other necessary variables to be created. For each subject there will be nine records associated with nine visits: Baseline and Visit 3 - Visit 10. The ADEFF2 analysis dataset will be created based on MI assuming MNAR for sensitivity analysis and MI assuming MAR for secondary analyses. The ADEFF2 will contain 100 imputations of each record of each visit for the variables in ADEF1 with IMPUTNR variable.

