6.2 Visit Windows

The Visit windows depicted in the table below will be used to evaluate subject compliance with scheduled visits with respect to protocol deviation. However, no visit windows will be used for statistical analysis; data will be analyzed according to the scheduled visit they are associated with in the CRF.

Table 2: Visit Windows and Study Day Ranges

Week	Day	Visit Window
0 (Visit 1-2)	1	<= Day 1
1 (Visit 2-3)	7	Day 2 - Day 9
2 (Visit 3-4)	14	Day 10 - Day 16
3 (Visit 4-5)	21	Day 17 - Day 23
4 (Visit 5-6)	28	Day 24 - Day 30
5 (Visit 6-7)	35	Day 31 - Day 37
6 (Visit 7-8)	42	Day 38 - Day 44
7 (Visit 8-9)	49	Day 45 - Day 51

8 (Visit 9-10)	56	Day 52 - Day 58
----------------	----	-----------------

For analysis by titration and maintenance period, the periods will be defined as follows: Titration period: First dose date \leq to \leq v5 date; Maintenance period: V5 date $<$ to \leq V10 date.

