6.3.3 Intent-to-treat (ITT) population

All randomized subjects who received at least 1 dose of study drug and have a baseline and at least one post-randomization ADHD-RS-5 assessment. Subjects will be analyzed according to the treatment to which they were randomized.

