6.6 Handling Missing Data

6.6.1 Missing Efficacy Variables

Missing items in ADHD-RS-5 scale

1. If more than 3 items of ADHD-RS-5 have missing or invalid data, the total score will be set to missing. If the total score is missing then both subscales (inattention or Hyperactivity/Impulsivity) will be set to missing.
2. If 3 items of ADHD-RS-5 or less have missing or invalid data, the values for the missing items will be imputed using the mean of the non-missing items rounded to the nearest integer.

With respect to the primary analysis, missing ADHD-RS-5 Total Scores will be assumed to be missing at random (MAR) (*See Panel on Handling Missing Data in Clinical Trials, (2010) National Research Council: The Prevention and Treatment of Missing Data in Clinical Trials*) that is, given the observed data, the reason for the missing data does not depend on the unseen data. The Mixed Model for Repeated Measures (MMRM) method, implemented via SAS® PROC MIXED (SAS/STAT Software), will be used for handling missing ADHD-RS-5 Total Scores under MAR assumption. The motivation behind MMRM is to solve the issue of addressing an on-treatment question, i.e. what happens if a typical subject completes their assigned treatment. MMRM does this by conditioning on the previous observations and other covariates that may inform on both missingness and outcome.

A sensitivity analysis will be performed by assuming missing ADHD-RS-5 Total Scores are not missing at random (MNAR) ([Yang, 2014](#)), that is, the probability that an observation is missing may depend on its underlying unobserved value. This will be implemented using SAS® PROC MI and SAS® PROC MIANALYZE (SAS/STAT Software).

For secondary endpoints, missing values will be assumed as missing at random (MAR). Missing data will be imputed using SAS® PROC MI (SAS/STAT Software).

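### The rule that an early-termination visit counts as Visit 10 has no efficacy exception, so an early-termination ADHD-RS-5 score probably enters the primary and sensitivity analyses as an observed Week 8 value

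*SAP*

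**What the plan says.** SAP 6.1 treats the ET visit as follows: it "for early discontinued subjects will be assumed to correspond to Visit 10 for statistical summaries but displayed as is in listings". The only contrast drawn is with listings; no type of variable or analysis is excepted.

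Several other places bear on how far the rule reaches:

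- The list of abbreviations defines EOS as the Visit 10 date or, for dropouts, the date of the last visit. Footnote i to Table 1 agrees.
- Section 3.3 has early dropouts complete all Week 8 procedures, so ET scores will exist on every efficacy scale.
- Section 6.1 on ADEFF1: "For each subject there will be nine records associated with nine visits: Baseline and Visit 3 - Visit 10". There is no separate ET record.
- Section 6.2: "no visit windows will be used for statistical analysis; data will be analyzed according to the scheduled visit they are associated with in the CRF".
- Sections 6.13.1 and 6.14 label their endpoints as Week 8 (EOS).

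On missing data, 6.6.1 says that the MMRM addresses "what happens if a typical subject completes their assigned treatment". Section 6.13.2 imputes missing scores on the premise that active-arm subjects follow the placebo outcome model after discontinuation. Section 6.14 imputes missing Week 8 values of secondary endpoints from treatment and baseline.

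**The concern.** If the ET score fills the Week 8 cell, the methods above see an observed value there and leave it alone. The Week 8 contrast then mixes true Week 8 outcomes with scores taken earlier, some of them during titration, since the 400 mg arm reaches its dose only at the Week 3 visit (3.1). For dropouts with an ET visit, the primary endpoint becomes a last-visit endpoint, which is a different question from the one in 6.6.1. The placebo-based analysis, described as a worst case, would not touch those subjects' Week 8 values; only their skipped intermediate weeks would be imputed.

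With equal dropout, a real effect is diluted. With unequal dropout, a difference can appear where there is none, in favour of the arm that loses fewer subjects.

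**Working it through.** **1. The plan's own figures.** With effect 0.547, two-sided alpha 0.05 and a t-test, power is 0.899 at 71 per arm and 0.903 at 72, so the stated 72 reproduces. Then 72/(1 - 0.279) = 99.86, rounded up to 100 per arm. Both inputs used below, 27.9% and 0.547, come from SAP 3.5.

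**2. Values exposed.** Expected non-completers: 0.279 x 300 = 83.7; completers: 216.3. Let a be the share of non-completers with an ET score (assumed).

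| | a = 0.5 | a = 1 |
|---|---|---|
| Early scores among Week 8 values, 83.7a/(216.3 + 83.7a) | 41.9/258.2 = 16.2% | 83.7/300 = 27.9% |
| Week 8 values left to impute, 83.7(1 - a) | 41.9 | 0 |

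**3. Effect on the Week 8 mean.** In an arm with dropout d and true Week 8 change m, the mean of the available Week 8 values is

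m x [(1 - d) + d·a·f] / [(1 - d) + d·a],

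where f is the mean fraction of the Week 8 change already reached at the ET visit. Assumed values of f, with dropout over Weeks 1-7 either uniform or weighted to early weeks (in proportion to 8 - k for week k):

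| Onset | Uniform | Early-weighted |
|---|---|---|
| Linear to Week 8 | 0.500 | 0.375 |
| Linear to a plateau at Week 4 | 0.786 | 0.661 |
| 1 - exp(-k/2), scaled to 1 at Week 8 | 0.801 | 0.710 |

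**4. Equal dropout, d = 0.279.**

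- a = 0.5, f = 0.375: 0.547 x (0.721 + 0.1395 x 0.375)/0.8605 = 0.492. With f = 0.801: 0.529.
- a = 1, f = 0.375: 0.547 x (0.721 + 0.279 x 0.375) = 0.452. With f = 0.801: 0.517.

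**5. Unequal dropout, 32.9% v 22.9%.** Placebo change is assumed at 0.5-1.0 SD, with the same onset in both arms.

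| | a = 0.5 | a = 1 |
|---|---|---|
| True 0.547, more dropout on active | 0.44-0.52 | 0.37-0.50 |
| True 0.547, more dropout on placebo | 0.52-0.55 | 0.50-0.54 |
| True 0, false difference | 0.01-0.04 | 0.01-0.06 |

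For example, at a = 1 the false difference is m x 0.10 x (1 - f): from 0.5 x 0.10 x 0.199 = 0.01 to 1.0 x 0.10 x 0.625 = 0.06.

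**6. Check in a repeated-measures model.** The formula averages available Week 8 values, whereas an MMRM also uses earlier visits. A large simulation (40,000 per arm, unstructured covariance in the fitted model) therefore checked it. It assumed SD 1, AR(1) correlation 0.8, a placebo change of 1 SD, MAR dropout over Weeks 1-7 and an ET score for every dropout.

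| 27.9% dropout in both arms | True value in the sample | ET score as Visit 10 | ET score at its own week |
|---|---|---|---|
| Linear onset | 0.536 | 0.454 | 0.539 |
| Early plateau | 0.532 | 0.480 | 0.533 |

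In all ten scenarios run, keeping the ET score at its own week came within about 0.005 SD of the true value.

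**The case against.** The strongest reply is that the rule may never have been meant for the models. The sentence before it reads "Unscheduled measurements will be excluded from the descriptive statistics and statistical analysis but will be included in listings", so 6.1 knows the difference between description and analysis, and the rule itself speaks only of statistical summaries. The specific sections on the MMRM and on imputation presuppose missing scores after dropout, and specific text usually governs general text. This stands as a possible reading, which is why the wider one is called likelier and not certain. It is less likely because the EOS definition, footnote i, the ADEFF1 structure and the ban on windows all point the other way. It also leaves a gap: a subject qualifies for the ITT population if they "have a baseline and at least one post-randomization ADHD-RS-5 assessment", and if the only such score is from the ET visit, ADEFF1 has no stated record for it. That is an edge case, and the dataset specifications still to be written might settle it.

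A second reply is that the EOS definition shows a deliberate last-visit convention. If so, the conflict with 6.6.1 and 6.13.2 remains unreconciled.

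A third is that the effect is small. Attendance of 100% is implausible when loss to follow-up and withdrawn consent are among the listed reasons for leaving. Section 3.2 also follows treated subjects "regardless of the number of doses of SM taken, unless consent for follow-up is withdrawn", which could reduce early ET visits. Half attendance with equal dropout costs 3-10% of the effect, against the drug. A false difference of 0.04 SD with 100 per arm moves a two-sided 5% z-test to about 6%, and 0.06 SD to about 7%. These points are fair and limit the weight of the finding.

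A reader might infer that all of a dropout's Week 1-7 scores are analysed as Week 8. The text does not support that: only the ET-visit score moves, one per scale, and earlier scheduled scores stay at their own visits. Nor does the rule contradict MAR for values that remain missing; the conflict is with the complete-treatment question.

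**Conclusion.** The point holds in limited form. As written, 6.1 allows, and on the likelier reading requires, that an ET-visit ADHD-RS-5 score be treated as an observed Week 8 value in the primary MMRM and the placebo-based imputation. That conflicts with 6.6.1 and with the premise of 6.13.2, and it removes those Week 8 values from the plan's only missing-data sensitivity analysis.

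The sizes rest on 27.9% and 0.547 from the SAP. ET attendance, onset, dropout timing, placebo change and the ten-point imbalance are assumptions. Equal dropout is a dilution and so conservative; unequal dropout can err in either direction. No loss of power below the planned 90% is claimed, because filling Week 8 cells also raises the number of values analysed. The per-protocol analysis is unaffected, since 6.3.4 requires all ten visits. The matter should be settled before database lock.

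**What to change.** - **Primary and sensitivity analyses.** In 6.1, state that ET = Visit 10 does not apply to the ADHD-RS-5 total-score MMRM or the MNAR imputation. For these, assign the ET score to the scheduled visit whose Table 2 window contains its study day, and assign any ET score on Day 52 or later to Visit 10. Fix in advance a tie rule for an ET score and a scheduled score in the same window. Otherwise leave Week 8 missing.
- **Section 6.2.** Amend the sentence on visit windows to permit this one use.
- **Secondary endpoints** (CGI-I, responder rate, ADHD-RS-5 subscales, Conners 3, WFIRS-P, PSI-4-SF). State whether an early ET score counts as Week 8 (EOS) or is imputed under 6.14, reconcile that with the EOS definition, and report the other approach as supplementary.

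The cost is wording and one derivation rule, with no new data. The Week 8 standard error becomes slightly larger, and the no-windows decision gains a limited exception. If the secondary endpoints are imputed, early ET scores drop out of those analyses, because the 6.14 imputation uses only treatment and baseline. For Conners 3, WFIRS-P and PSI-4-SF the ET score is a dropout's only post-baseline value, so that choice is debatable and is left to the sponsor to state.

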6.2 Visit Windows

The Visit windows depicted in the table below will be used to evaluate subject compliance with scheduled visits with respect to protocol deviation. However, no visit windows will be used for statistical analysis; data will be analyzed according to the scheduled visit they are associated with in the CRF.

Table 2: Visit Windows and Study Day Ranges

Week	Day	Visit Window
0 (Visit 1-2)	1	<= Day 1
1 (Visit 2-3)	7	Day 2 - Day 9
2 (Visit 3-4)	14	Day 10 - Day 16
3 (Visit 4-5)	21	Day 17 - Day 23
4 (Visit 5-6)	28	Day 24 - Day 30
5 (Visit 6-7)	35	Day 31 - Day 37
6 (Visit 7-8)	42	Day 38 - Day 44
7 (Visit 8-9)	49	Day 45 - Day 51

8 (Visit 9-10)	56	Day 52 - Day 58
----------------	----	-----------------

For analysis by titration and maintenance period, the periods will be defined as follows: Titration period: First dose date \leq to \leq v5 date; Maintenance period: V5 date $<$ to \leq V10 date.

6.3 Analysis populations

6.3.1 Randomized population

All enrolled subjects that had a Baseline Visit scheduled and are randomized via the IWRS.

6.3.2 Safety population

All subjects randomized into the study, who received at least 1 dose of SM. Subjects will be analyzed according to the treatment they received.

6.3.3 Intent-to-treat (ITT) population

All randomized subjects who received at least 1 dose of study drug and have a baseline and at least one post-randomization ADHD-RS-5 assessment. Subjects will be analyzed according to the treatment to which they were randomized.

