6.13 Efficacy Analyses

The efficacy analyses will be based on the ITT population and will be performed on ADHD-RS-5 total score, Conners 3-PS composite T score, Conners 3-SRS composite T score, WFIRS-P total score and PSI-4-SF total scores.

All confidence intervals, statistical tests, and resulting p-values will be reported as two-sided and will be assessed at the 5% significance level and interactions at 10%.

With respect to Analysis of Covariance, the Gamma regression will be used on the original scale, if the normality assumption for the standard ANCOVA model is not met based on diagnostic residual plots based on the data before imputation.

Multiplicity will be adjusted for the primary endpoint and key secondary endpoints.

The mean profiles of ADHD-RS-5 total score, Conners 3-PS composite T score, Conners 3-SRS composite T score, WFIRS-P total score, PSI-4-SF score and CGI-I score will be presented graphically by treatment group and scheduled study visit. In addition, plots of the Cumulative Distribution Functions of Change from Baseline in ADHD-RS-5 will be presented (Figures 14.2.1.1 - 14.2.6.2)

For supportive analysis, the absolute value and change from baseline to Week 8 (EOS) of all efficacy variables will be summarized using descriptive statistics by treatment group and visit (Tables 14.2.5.1- 14.2.5.6).

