6.13.2 Sensitivity Analysis

The sensitivity analysis assumes that missing ADHD-RS-5 Total Scores are missing not at random (MNAR), that is, the probability that an observation is missing may depend on its underlying unobserved value. (For example, the probability of missing ADHD-RS-5 Total Score at Week 8 is not related to the observed ADHD-RS-5 Total Score at visit 9). Placebo-based multiple imputation will be used to fill in missing values. This approach may be considered “worst-case” sensitivity analyses as it assumes that after discontinuation, subjects from the active treatment arms would adopt the outcome model estimated from the placebo arm. The placebo-based imputation will be implemented by adopting the following three steps.

- 1) SAS PROC MI (SEED=220877) is applied to the input dataset containing all by-visit ADHD-RS-5 Total Score during the baseline, titration, and maintenance period. Multivariate imputation will be carried out by the fully conditional specification (FCS) method. One hundred (100) multiply-imputed datasets will be created. SAS® PROC MI with the MNAR statement will be implemented by using the following SAS code.

```
PROC MI DATA= EFF NIMPUTE=100 SEED=220877 OUT=MNAROUT
  CLASS TREATMENT;
  VAR BASE WK1– WK8(EOS);
  FCS REG;
  MNAR MODEL (BASE WK1– WK8 (EOS))/MODELOBS= (TREATMENT='A');
  RUN;
```

In the above SAS code, EFF denotes the efficacy data set, Base, WK1– WK8 are analysis values of ADHD-RS-5 total at baseline and each of treatment weeks from Week 1 (at Visit 3) to Week 8 (at Visit 10), and treatment = ‘A’ denotes Placebo.

2. For each of the multiply-imputed data sets, CFB to EOS will be computed. For each imputation, the CFB will be analyzed using ANCOVA model, which will include fixed effect terms for treatment and baseline ADHD-RS-5 Total Score as a covariate. Each of the treatment groups (SPN-812 ER 200 mg and 400 mg) will be compared with the Placebo. The LS means of treatment groups, differences between the LS means of treatment groups and placebo, 95% confidence intervals around the differences and p-value will be computed.
3. Finally, to combine estimates (LS means, treatment LS mean differences, 95% CI around the difference and p-value) from the 100 datasets, SAS® PROC MIANALYZE will be used.

The summary of sensitivity analysis will be presented in Table 14.2.1.2. The corresponding full SAS output will be presented in Listing 16.1.9.2.

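### The placebo-based sensitivity analysis runs on an ITT set that excludes dosed children with no post-baseline ADHD-RS-5, so it never imputes them

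*SAP*

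**What the plan says.** Three parts of the SAP have to be read together.

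- Section 6.3.3 defines the ITT set as follows: "All randomized subjects who received at least 1 dose of study drug and have a baseline and at least one post-randomization ADHD-RS-5 assessment".
- Section 6.13 states: "The efficacy analyses will be based on the ITT population". Section 6.13.2 falls under that heading and names no wider population.
- Section 6.13.2 explains the placebo-based imputation this way: "This approach may be considered “worst-case” sensitivity analyses as it assumes that after discontinuation, subjects from the active treatment arms would adopt the outcome model". The model in question is the one fitted to the placebo subjects. Its input is a data set "containing all by-visit ADHD-RS-5 Total Score during the baseline, titration, and maintenance period". The SAS code lists BASE and Weeks 1 to 8 as the variables and restricts the imputation model to the placebo arm.

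Two other provisions bear on who is affected. Section 3.3 says: "All subjects who discontinue early will complete the procedures listed for Week 8 (EOS"), and Table 1 includes the ADHD-RS-5 among those procedures. Section 6.1 treats the early-termination visit as Visit 10 in statistical summaries.

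**The concern.** An analysis offered as the conservative check on withdrawal should cover the children to whom its assumption applies most fully. A child who stops before any post-baseline rating has no on-drug score at all. Under the placebo-based rule, that child's whole course would be drawn from the placebo model given baseline. Section 6.3.3 removes exactly these children before imputation starts, and it does so on the basis of something that happens after randomisation.

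At stake is how far the worst-case label can be trusted. Without these children, the placebo-based difference is estimated only among those who stayed long enough to be rated at least once. No efficacy analysis in the readable text covers everyone randomised and dosed; the redacted exploratory analyses are not counted either way.

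**Working it through.** **Step 1: who is excluded.** Take a dosed child with a baseline score who discontinues.

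| Situation | In ITT? | Week 8 value in the placebo-based MI |
|---|---|---|
| Rated at Visit 3 or later, then lost | Yes | Imputed |
| Leaves early, attends early-termination visit | Yes | Observed if the Visit 10 mapping of 6.1 extends to the imputation data, otherwise imputed |
| Never rated after baseline | No | Not in the analysis |

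Only the third row is excluded by the ITT definition. The SAP does not settle the second row.

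**Step 2: does it matter for the MMRM?** No. The outcome is change from baseline at each visit. A child with no post-baseline score has no change value and contributes no record.

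**Step 3: does it matter for the placebo-based MI?** Yes. BASE is in the variable list, so a baseline-only record can be imputed. Let f_a and f_p be the shares without a post-baseline score in an active arm and on placebo, and let m_a and m_p be the mean changes among those now in ITT. Assume that imputation from the placebo model gives an excluded child an expected change of m_p.

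- Active arm, wider set: (1 − f_a)·m_a + f_a·m_p
- Placebo arm, wider set: (1 − f_p)·m_p + f_p·m_p = m_p
- Difference: (1 − f_a)·(m_a − m_p)

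The placebo share cancels. The dilution depends on the active-arm share alone.

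**Step 4: the plan's own figures.** Section 3.5 gives an effect size of 0.547, two-sided alpha of 0.05, 90% power, 72 per arm in ITT and 27.9% non-completion. A two-sample t-test with the noncentral t gives 90.3% power at 72 per arm and 89.9% at 71, so 72 reproduces. Inflation gives 72 / (1 − 0.279) = 99.9, so 100 per arm also reproduces.

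**Step 5: size.** The SAP does not state the share f, so the values below are assumptions.

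- f = 2%: 0.547 × 0.98 = 0.536
- f = 5%: 0.547 × 0.95 = 0.520
- f = 8%: 0.547 × 0.92 = 0.503

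For power, assume the same f in all arms and an unchanged SD. Compare 100·(1 − f) per arm at 0.547 (excluded) with 100 per arm at 0.547·(1 − f) (included).

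| f | Effect if included | Power, excluded | Power, included |
|---|---|---|---|
| 2% | 0.536 | 96.8% | 96.5% |
| 5% | 0.520 | 96.3% | 95.5% |
| 10% | 0.492 | 95.4% | 93.4% |
| 27.9% | 0.394 | 90.3% | 79.3% |

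The last row is only a bound. It would require every non-completer to have no post-baseline score.

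**The case against.** **The definition is explicit, pre-specified and harmless to the primary analysis.** This stands. Nothing in the SAP contradicts section 6.3.3, and only one sensitivity analysis is affected.

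**Using the same population is a virtue.** Section 6.6.1 presents the sensitivity analysis as a change from a missing-at-random to a not-at-random assumption. If the population changed as well, a difference from the MMRM could not be attributed to either change. This is a good reason not to replace the ITT run. It is no reason against adding a second run.

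**The group is narrow.** Ratings are weekly from Day 7, and early discontinuers are to complete the Week 8 procedures. A reader might infer that early dropouts in general escape imputation because of the ITT rule. The SAP does not support that: a child who attends the early-termination visit is in ITT. The exclusion reaches only children who never return. It need not be empty, because section 3.3 lists loss to follow-up and withdrawal of consent among the reasons for stopping.

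**The bias might need more early loss on active than on placebo.** A reader might infer this too, but the algebra in Step 3 does not bear it out. Equal early loss in all arms produces the same dilution.

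**The numbers are assumed and the starting value is generous.** This also stands. The 0.547 is the Phase IIb planning value for 200 mg on the ADHD-RS-IV, not a placebo-based estimate, which later dropouts would already have reduced. What carries over is the factor (1 − f_a), not the absolute figures.

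**Disposition is already reported.** Table 14.1.1.1 gives the safety and ITT sets with reasons for discontinuation. The excluded children can largely be derived from the difference between the two sets.

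**Conclusion.** The point holds in a limited form. Dosed children with a baseline but no post-baseline ADHD-RS-5 are not imputed in the placebo-based analysis, although its model could impute them. The resulting estimate is too favourable to the drug by a proportion equal to their share of the active arm. For shares of 2% to 8% the effect shrinks by the same 2% to 8%; at 10%, power with 100 per arm would still be 93.4%. With no such children there is no effect.

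This rests on three assumptions: an imputed active-arm child has zero expected difference from placebo, the SD is unchanged, and the share is a guess because the SAP gives none. The 27.9% non-completion figure should not be read as that share, since most non-completers may have at least one rating. The documents support no claim that the primary result is biased. This is a desirable refinement.

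**What to change.** - Leave section 6.3.3 as it is for the MMRM.
- In section 6.13.2, keep the ITT run of the placebo-based imputation, so that one comparison with the MMRM keeps the population fixed.
- Add to section 6.13.2 that the same imputation is also run on all randomised children who took at least one dose and have a baseline ADHD-RS-5, with or without a later score, analysed by randomised arm.
- State in section 6.13.2 whether an early-termination score mapped to Visit 10 under section 6.1 enters the imputation as an observed Week 8 value. Widening the population does not resolve this.

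The cost is two sentences, one extra run and a slightly smaller sensitivity estimate. No new data are needed, the testing sequence is untouched, and Table 14.1.1.1 needs no change. The text should be settled before database lock.
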